5.1. Schedule of examinations and procedures

5.1.1. Screening examinations before treatment

1. Magnetic resonance imaging (MRI) of the brain

Note: Time from MRI to start of radiotherapy has to be ≤ 14 days

2. Performance status assessment

ECOG / KPS

**3. Assessment of Adverse Events before treatment
(Medical history relevant for the study)**

NCI CTCAE v5.0

4. Assessment of Quality of Life

EORTC QLQ-C30

EORTC QLQ-BN20

5. Assessment of RPA and GPA prognostic scores

6. Documentation of glucocorticoid dose

**7. Documentation of systemic treatment including prior
systemic therapies**

8. Written informed consent

9. Pregnancy test in women of childbearing potential

Pregnancy should be ruled out by determining Serum β -HCG

10. Planning CT

5.1.2. Examinations immediately after radiotherapy

A deviation from the last day of radiotherapy up to ± 2 days due to organizational reasons is acceptable. With SRS the examination has to take place after the treatment was administered, however.

1. Performance status assessment

ECOG / KPS

2. Assessment of Adverse Events

NCI CTCAE v5.0

3. Assessment of Quality of Life

EORTC QLQ-C30

EORTC QLQ-BN20

4. Documentation of glucocorticoid dose

5. Documentation of systemic treatment

5.1.3. Final examination

6 weeks after the last radiation treatment. A deviation from the exactly specified date of up to ± 1 week is acceptable. If one follow-up examination is delayed, the date of the next follow-up examination should not be postponed but should be conducted at the specific prespecified date following radiotherapy.

1. Magnetic resonance imaging (MRI) of the brain

**2. Performance status assessment**

ECOG / KPS

3. Assessment of Adverse Events

NCI CTCAE v5.0

4. Assessment of Quality of Life

EORTC QLQ-C30

EORTC QLQ-BN20

5. Documentation of glucocorticoid dose**6. Documentation of systemic treatment****5.1.4. Follow-up examinations**

3 months after radiotherapy, then every 3 months up to a period of 2 years after the last radiation treatment. A deviation from the exactly specified date of up to ± 2 week is acceptable. If one follow-up examination is delayed, the date of the next follow-up examination should not be postponed but should be conducted at the specific prespecified date following radiotherapy.

1. Magnetic resonance imaging (MRI) of the brain**2. Performance status assessment**

ECOG / KPS

3. Assessment of Adverse Events

NCI CTCAE v5.0

4. Assessment of Quality of Life

EORTC QLQ-C30

EORTC QLQ-BN20

5. Documentation of glucocorticoid dose**6. Documentation of systemic treatment**

5.2. General health status assessment

The KPS Index and ECOG Performance Status will be used to assess each patient's general health status. (Table 5)

Table 5: Performance Scales

Karnofsky Status	Karnofsky Grade	ECOG Grade	ECOG Status
Normal, no complaints	100	0	Fully active, able to carry on all pre-disease performance without restriction
Able to carry on normal activities. Minor signs or symptoms of disease	90	0	Restricted in physically strenuous activity but ambulatory and able to carry out work of a light or sedentary nature, e.g., light housework, office work
Normal activity with effort	80	1	Restricted in physically strenuous activity but ambulatory and able to carry out work of a light or sedentary nature, e.g., light housework, office work
Care for self. Unable to carry on normal activity or to do active work	70	1	Ambulatory and capable of all selfcare but unable to carry out any work activities. Up and about more than 50% of waking hours
Requires occasional assistance, but able to care for most of his needs	60	2	Ambulatory and capable of all selfcare but unable to carry out any work activities. Up and about more than 50% of waking hours
Requires considerable assistance and frequent	50	2	Capable of only limited selfcare, confined to bed or chair more than 50% of waking hours
Disabled. Requires special care and assistance	40	3	Capable of only limited selfcare, confined to bed or chair more than 50% of waking hours
Severely disabled. Hospitalization indicated	30	3	Completely disabled. Cannot carry on any selfcare. Totally confined to bed or chair
Very sick. Hospitalization necessary. Active supportive	20	4	Completely disabled. Cannot carry on any selfcare. Totally confined to bed or chair
Moribund	10	4	Completely disabled. Cannot carry on any selfcare. Totally confined to bed or chair

5.3. Recording of adverse events

The Common Terminology Criteria for Adverse Events for Adverse Events (CTCAE) Version 5.0 established by the National Cancer Institute (NCI) will be used for the documentation of adverse events (AEs). AEs will be recorded before radiotherapy, after the last radiation treatment, 6 weeks after the end of radiotherapy, 3 months after the end of radiotherapy, and then every 3 months for a follow-up period of 2 years.

For information on adverse event reporting according to CTCAE, see https://ctep.cancer.gov/protocolDevelopment/electronic_applications/docs/CTCAE_v5_Quick_Reference_5x7.pdf.

5.4. FSRT Trial examination schedule

The FSRT Trial examination schedule is depicted at page 5.

6. Ethical and legal requirements

6.1. Ethics review

This study will not be started before review and approval by the responsible ethics committees has been obtained.

6.2. Ethical conduct of the study

This study protocol (and any future amendments to it) is drafted (will be drafted) in accordance with the ethical principles in the current version of the Declaration of Helsinki (see <https://www.wma.net/what-we-do/medical-ethics/declaration-of-helsinki/>).

The study has been registered at ClinicalTrials.gov (www.clinicaltrials.gov NCT03697343) and at the German Clinical Trials Register (www.drks.de - DRKS00015647).

6.3. Informed consent

Before recruitment into the clinical trial each patient will be informed, that participation in the study is completely voluntary, and that he or she may withdraw the participation in the trial at any time without any declaration of reasons. This will not lead to any disadvantage for the respective patient. If the withdrawal is caused by any adverse events, the patient should inform the investigator about this fact. The investigator will inform the patient about the treatments to be used and their possible adverse effects. At the same time, he/she will be informed on the nature and objectives of the study, expected advantages of the participation, possible hazards of the study and alternatives of treatment. The patient will have sufficient time for his decision and opportunity to ask additional questions. Moreover, the patient will receive a written "Patienteninformation" (see Appendix), containing all relevant information for the patient's decision and the course of the study. The consent of the patient to participate must be obtained in writing before recruitment into the study. The informed consent form "Einwilligungserklärung" (see Appendix) must be dated and signed by the patient. Thereby, he declares his voluntary consent to participate in the study and his willingness to comply with the requirements of the trial and the instructions of the treating investigator during the course of the study. He also agrees that data on his disease are recorded within the framework of the clinical trial and that they are transferred in a pseudonymized way. Moreover, the patient agrees that delegates from the responsible authorities or the study management may have direct access to his/her original medical records for trial related monitoring, audit, review and regulatory inspection. The original informed consent form has to be stored in the Investigator Site

File. The patient receives a copy and one copy is filed in the patient's hospital documents. First, the patient has to date and sign the informed consent form. The investigator obtaining the informed consent has to date and sign the informed consent form after the patient. The informed consent is only valid after receiving the patient's signature.

The Patient Information Sheet, Informed Consent Form and all other documents to be issued to study participants will be submitted to the responsible ethics committee for approval prior to their use.

6.4. Subject data protection

Regulations of the data protection legislation are followed. It is assured that clinical and demographic data about study patients is always submitted and stored in a pseudonymized manner. Each study patient is identified by a pseudonym. Study patients must be informed about the transfer of their pseudonymized data. The identifying personal information about a patient is retained at the Trial office. Only the investigator or administrative staff is able to reveal a pseudonym. In accordance to the guidelines of the Ethics Committees initials are considered as personal information, are never transmitted and remain at the medical site. Persons that do not consent to transfer of their pseudonymized data will not be included in the study.

6.5. Audits and inspections

In case of an audit by the study management or an appropriate authority the investigator will make available all relevant documents. If an audit visit by a regional authority is announced, the respective center should inform the coordinating investigator as early as possible to allow for an appropriate preparation and support. The inspected investigator or organizational institution of the study will be informed on the result of the audit.

Internal quality reviews will take place at the meetings of the study participants. Therefore, the reference board will instruct the participating centers to present their primary documentation of study procedures. The results will be discussed at the meetings to improve the quality of procedures and documentation.

6.6. Documentation

All the data retrieved during the conduct of the study are entered into the appropriate electronic case record forms (eCRF) by the investigator or another person authorized by the investigator in a timely manner.

6.7. Data Management

The Medical Center for Information and Communication Technology (MIK) and the Winicker Norimed GmbH will develop and validate the study database according to its Standard Operating Procedures prior to the start of data entry. The data management system is based on commercial

research software that stores the data in a database. All changes made to the data are stored in an audit trail. The study software has a user and role concept that can be adapted to the specific needs of the study. The database is integrated into a general IT infrastructure and security concept that has a firewall and a backup system. Daily backups of the data will be performed. After data completion and cleansing, the database will be closed and the data exported for statistical analysis.

6.8. Data storage

All relevant study documents including the eCRFs are stored at the office of the coordinating investigator/sponsor for 30 years in accordance with the German X-ray Ordinance (RöV) or Radiation Protection Ordinance (StrlSchV). The investigators have to archive major administrative documents (correspondence with ethical committee, authorities, sponsor etc.), the patient identification log, the signed informed consent forms, and the main study documents (protocol, amendments) for the same time period. The original patient records have to be archived according to the standard procedures of the respective institution, but at least for 30 years. The patient identification list will be stored separate from the documentation records.

6.9. Handling and documentation of pregnancies

Pregnant and breastfeeding women are generally excluded from participating in this study. If a female patient or the female partner of a male patient should become pregnant during the treatment period or within 6 months after the last study treatment, the responsible investigator must document this in the patient records and inform the principal investigator accordingly. Pregnant study participants must end their participation in the clinical trial immediately. The pregnancy must be monitored and documented throughout the full course of pregnancy and up to 8 weeks after birth. The attending gynecologist may be consulted, as needed; the participant's consent is required for this.

6.10. Contraception

For this trial, male subjects will be considered to be of non-reproductive potential if they are permanently sterile by bilateral orchidectomy.

Female subjects will be considered of non-reproductive potential if they are either:

- postmenopausal (defined as at least 12 months with no menses without an alternative medical cause; in women < 45 years of age a high follicle stimulating hormone (FSH) level in the postmenopausal range may be used to confirm a post-menopausal state in women not using hormonal contraception or hormonal replacement therapy. In

the absence of 12 months of amenorrhea, a single FSH measurement is insufficient.)

- have had a hysterectomy and/ or bilateral oophorectomy and/ or bilateral salpingectomy, at least 6 weeks prior to screening.

Female and male subjects of reproductive potential must agree to avoid becoming pregnant or impregnating a partner, respectively, from screening to 90 days after the last administration of radiotherapy by complying with one of the following:

1) practice abstinence* from heterosexual activity

OR

2) use of highly effective contraception during heterosexual activity by both themselves and their partners with reproductive potential.

*Abstinence (relative to heterosexual activity) can be used as the sole method of contraception if it is consistently employed as the subject's preferred and usual lifestyle. Periodic abstinence (e.g., calendar, ovulation, symptom-thermal, post-ovulation methods, etc.) and withdrawal are not acceptable methods of contraception.

Methods of contraception for females with childbearing potential must be highly effective. The following methods are allowed:

- 1) combined (estrogen and progestogen containing) hormonal contraception associated with inhibition of ovulation:
 - oral
 - intravaginal
 - transdermal
- 2) progestogen-only hormonal contraception associated with inhibition of ovulation:
 - oral
 - injectable
 - implantable
- 3) intrauterine device (IUD)
- 4) intrauterine hormone-releasing system (IUS)
- 5) bilateral tubal occlusion

Required highly-effective contraception methods for men are:

- 1) Bilateral vasectomy (after medical assessment of surgical success)
- 2) Condoms + spermicidal agent

6.11. Withdrawal by the subject

Subjects are free to withdraw from the study at any time with or without explaining the reason(s) for withdrawal and without incurring any disadvantages from withdrawal. The responsible investigator must document the date of withdrawal, the data collected up until the point of withdrawal, and the reason(s) for withdrawal, if known. In a patient wishes to withdraw from study, the investigator should perform all examinations

normally conducted during the final study visit at the time of the last follow-up visit.

6.12. Withdrawal by the responsible study physician

Subjects must be withdrawn from the study in the event of:

- Adverse events that do not permit further treatment or which make further study participation seem inadvisable due to the low information value of the data collected
- Circumstances that make it impossible to adhere to schedule of examination visits specified in the study protocol
- Lack of adequate patient compliance.

7. Assessment of Efficacy

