2.4. Time schedule

Start of study:	Q3 2020
Start of recruitment:	Q1 2021
Duration of recruitment:	3 Jahre
Duration of follow-up:	2 Jahre
End of study:	2026

Follow-up is performed for progression/radionecrosis as well as for overall survival, toxicity and distant progression, respectively. In case of local progression, radionecrosis or distant progression, follow-up for the other events as well as toxicities and overall-survival continues. In case of radionecrosis, follow-up for progression continues, if not determined by histology, as progression can occur after a lesion has experienced radionecrosis. Conversely, in case of progression, follow-up for radionecrosis for the respective lesion ends.

3. Selection of study population

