9.1. Research question and hypothesis

The primary research question to be answered in this randomized controlled trial is whether FSRT (experimental arm) achieves significantly better local control than the "gold standard", single-fraction SRS (control group) in patients with large brain metastases. The time to local progression (TTLP) of the irradiated lesions will be used as the primary endpoint for efficacy. TTLP is defined as the time from randomization until the detection of progression as per the *RANO-BM* criteria (cf. Section 8.1 – 8.3). Patients will be censored if they have no signs of local progression at the time of last tumor monitoring during follow-up or at the onset of one of the following competing risk events not associated with, or preceded by local progression: death, lost to follow up, unauthorized non-protocol treatment of the target lesions. The following hypotheses will be tested:

H0: HR (FSRT vs. SRS as standard) ≥ 0

H1: HR (FSRT vs. SRS as standard) < 0

HR = Hazard ratio

One-sided testing of the primary endpoint will be performed based on the formulated hypotheses.

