9.2. Sample size calculation

On the basis of available retrospective and dose-response relationship data, it is expected that SRS will result in a 12-month local tumor control rate of approximately 65% and that FSRT can increase this rate to about 80% (cf. Section 1.4). This difference is considered to be clinically significant. A sample size of N=191 evaluable cases each in the experimental and control arm, respectively, corresponding to a total of 382 patients, is required to detect a significant difference i.e. an increase in TTLP at least this large at 12-month follow-up in a randomized comparison. The number of TTLP events to be observed is 82. This calculation is based on the following framework conditions:

- The risk of making a false claim of superiority of FSRT which actually does not exist is 2.5% (α error, one-sided).
- The success rate for identifying superiority of FSRT over the control arm which actually exists is 80% (power, $1-\beta$ error).
- Assuming an exponential decline of TTLP curves
- As this is a basically palliative setting with disseminated disease, it must be considered that about half of the patients will be dead at 12-month follow-up. Consequently, a considerable proportion of patients

will have a truncated follow-up in which no event related to the primary endpoint occurs. The extent of this quasi-drop-out process is estimated to be $\leq 50\%$ and is also assumed to be exponentially distributed over the 12 months.

- Duration of follow-up for all patients: at least 12 months or until the incidence of local progression.

Note: Due to patient entry kinetics during the planned recruitment, and due to the intended follow-up period of up to 24 months for each patient (cf. section 5.1.4), the follow-up periods for a considerably number of patients, mainly those randomized early, may be significantly longer than 12 months by the end of the study. This should result in an increase in the expected number of observed events, leading to a further increase in power of the study. Since this effect is difficult to quantify (especially due to death as a competing risk event), it is not taken into account in sample size calculation, to be on the safe side. Therefore, the recruitment period is not included among the parameters provided above.

Sample size estimates were calculated based on the method of LACHIN and FOULKES (Lachin et al. 1986), applying the software NSURV (idv, Gauting, Germany).

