9.3. Patient evaluation categories

If a major eligibility violation occurs, the affected subject will be excluded from the statistical analysis and classified as "ineligible" (in accordance with the ICH E9 statistical principles for clinical trials). Only case reports will be presented for these patients.

All other patients will be included in an intention-to-treat analysis of the primary endpoint. A per-protocol analysis including only those patients who fully completed radiotherapy according to protocol will also be performed, as a sensitivity analysis.

All patients who received at least one dose of radiation treatment according to protocol will be included in the toxicity analysis.

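### Section 6.12 requires withdrawal from the study, not only from treatment, and does not keep MRI and survival follow-up, so the primary analysis can suffer avoidable informative censoring, possibly unequal between arms

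*Protocol*

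**What the plan says.** Protocol section 6.12 is worded as an obligation: "Subjects must be withdrawn from the study in the event of" three circumstances. The first has two limbs: "Adverse events that do not permit further treatment or which make further study participation seem inadvisable". The other two are circumstances that prevent adherence to the visit schedule, and inadequate compliance. Nothing in 6.12 provides for imaging, toxicity, quality-of-life or survival follow-up afterwards. The closing examination in section 6.11 is written only for patients who themselves wish to withdraw.

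Other sections bear on this:

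- **Section 4.6** leaves interrupting, stopping or modifying radiotherapy to the radio-oncologist, who informs the study center. It does not mention leaving the study.
- **Section 7.4** scores a lesion that has already enlarged as progression if the patient dies, is lost or routine follow-up ends.
- **Section 8.1.3** requires adverse events to be followed until they resolve or stabilize.
- **Section 9.1** censors TTLP at the last tumor assessment without progression.
- **Section 9.3** sets aside patients with major eligibility violations and then states: "All other patients will be included in an intention-to-treat analysis of the primary endpoint". Completing radiotherapy matters only for the per-protocol sensitivity analysis.

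**The concern.** An intention-to-treat comparison needs outcomes on randomized patients whether or not they complete treatment. Section 9.3 puts non-completers in the primary analysis, while 6.12 stops their observation when an adverse event is the reason. They remain in the analysis set as early censored times. The log-rank test treats such censoring as unrelated to the risk of progression. Adverse events, missed visits and poor compliance may well be related to neurological decline, so that assumption is doubtful.

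The arms are also exposed differently. SRS is a single fraction per metastasis and FSRT is 12 daily fractions (section 4.4.5), so the limb about adverse events that prevent further treatment has far more room to act in FSRT. If the withdrawn patients differ in risk from those who stay, the hazard ratio and the type I error shift. Radionecrosis and survival data can be lost in the same way. A later analysis plan can model the missing outcomes but cannot recover them.

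**Working it through.** **1. The planned design.** Inputs from sections 9.1 and 9.2:

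- "SRS will result in a 12-month local tumor control rate of approximately 65% and that FSRT can increase this rate to about 80" percent;
- one-sided testing, with the risk of a "false claim of superiority of FSRT which actually does not exist is 2.5" percent;
- power 80%;
- about half of patients dead by 12 months, modelled as exponential loss;
- 12 months of follow-up.

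Hazards per year are λ₁ = −ln 0.65 = 0.431 (SRS), λ₂ = −ln 0.80 = 0.223 (FSRT) and η = −ln 0.50 = 0.693 (loss). The event probability is P(λ) = λ/(λ+η) × (1 − e^−(λ+η)), which gives 0.2587 and 0.1461, and 0.2050 at the mean hazard of 0.327. With φ(λ) = λ²/P(λ), the values are φ₁ = 0.717, φ₂ = 0.341 and φ(mean) = 0.522.

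Lachin–Foulkes: n = [1.96 × √(2 × 0.522) + 0.842 × √(0.717 + 0.341)]² / (0.431 − 0.223)² = 190.7 with unrounded values, so 191 per arm. The plan's 382 is reproduced, with power 80.1%. The same inputs give about 77 events rather than the stated 82. That is a separate matter and does not affect this point. The plan models one loss process, equal in both arms, with no allowance for arm-specific withdrawal.

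**2. What must be assumed.** The protocol gives no withdrawal rate under 6.12 and no link between withdrawal and progression. The range used here is 2% to 10% of FSRT patients withdrawn and none of SRS. Their hazard of progression is 0.5, 1 or 2 times that of the others.

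**3. Withdrawal unrelated to progression.** The same formula with 191 × (1 − w) FSRT patients gives power of 79.6%, 78.9% and 77.6% at w = 2%, 5% and 10%. The loss at 10% is 80.1 − 77.6 = 2.5 points.

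**4. Withdrawal related to progression.** Log-rank test simulated with no true difference:

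- 191 per arm, 12-month local control 65% in both arms, loss hazard 0.693;
- a fraction w in each arm has r times the hazard of the rest;
- only the FSRT members of that fraction are censored, at 0.02 years (about one week);
- unstratified, 10,000 runs per case, rejection if Z < −1.96.

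| Withdrawn from FSRT | r = 0.5 | r = 1 | r = 2 |
|---|---|---|---|
| 2% | 2.0% | 2.6% | 3.0% |
| 5% | 1.9% | 2.5% | 3.7% |
| 10% | 1.2% | 2.4% | 5.5% |

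The simulation error near 2.5% is √(0.025 × 0.975 / 10,000) = 0.16 points. A repeat with another random seed gave 3.7% and 5.5% for r = 2, and 1.5% and 1.4% for r = 0.5, at 5% and 10% withdrawn. At r = 0.5 with 10% withdrawn, power under the planned effect falls to about 73%.

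**5. The same on the hazard-ratio scale.** Take a 20% one-year failure risk in both arms, so no true effect. FSRT then has 191 × 0.1461 = 27.9 events over 27.9 / 0.2231 = 125.1 person-years. Now remove 5% of patients (9.55) from the start:

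- With 50% one-year risk they take out 9.55 × 0.375 = 3.58 events and 3.58 / 0.693 = 5.17 person-years. Apparent HR = (24.33 / 119.9) / 0.2231 = 0.91.
- With 10% one-year risk they take out 9.55 × 0.0726 = 0.69 events and 0.69 / 0.1054 = 6.58 person-years. Apparent HR = (27.22 / 118.5) / 0.2231 = 1.03.

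The sign of the bias depends on who is withdrawn.

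**The case against.** The strongest reply is that 6.12 does not contradict the primary analysis. Section 9.3 defines who is analysed, 9.1 defines how they are censored, and withdrawn patients stay in the set. That is correct: the analysis set is intact, and the damage is to the follow-up that feeds it.

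Mitigating text also exists. Under 7.4 a patient whose lesion has already enlarged is scored as progression rather than censored when follow-up ends. This does not help patients withdrawn before enlargement was imaged, and withdrawal may remove the later imaging that could have reclassified the lesion as radionecrosis. Section 8.1.3 keeps adverse events under observation, so toxicity follow-up is not wholly lost. Where visits are truly impossible, MRI is lost whatever 6.12 says, and rewording would mainly save survival status.

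Three stronger readings are tempting but not supported:

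- **That the first trigger applies only to FSRT.** Its second limb, adverse events that make participation inadvisable, applies in either arm at any time, as do the other two triggers. Only the first limb of one trigger is largely specific to FSRT.
- **That the rule flatters FSRT.** The HR of 0.91 in the working is right for its inputs, but these are assumed, confined to FSRT and limited to high-risk patients. Lower-risk withdrawals reverse the sign.
- **That section 2.4 contradicts 6.12 by saying "follow-up for the other events as well as toxicities and overall-survival continues".** That sentence concerns patients who have had local progression, radionecrosis or distant progression. It does not address withdrawal.

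**Conclusion.** The point holds as a risk that the protocol creates and could avoid. Section 6.12 orders withdrawal from the study where ending treatment would suffice, secures no further outcome data, and so weakens the intention-to-treat comparison. The censoring can be informative and can differ between arms. The documents do not show that it will, how much, or in whose favour.

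Under assumed FSRT-only early withdrawal of 5% to 10%, the one-sided type I error would be about 3.7% to 5.5% at twice the hazard and about 1.9% to 1.2% at half. If withdrawal is unrelated to progression, type I error is essentially unchanged and 10% withdrawal costs 2.5 points of power. Withdrawals in both arms, or later ones, would give different figures. No effect on radionecrosis or survival was calculated. Severity: should be fixed.

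**What to change.** Amend 6.12 so that ending protocol treatment and ending study follow-up are separate. After treatment ends for any reason, the scheduled MRI, toxicity, quality-of-life and survival follow-up should continue as far as feasible to 24 months unless consent is withdrawn. Where visits are impossible, at least survival status should be collected. State that these patients stay in the intention-to-treat analysis.

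Reconcile 6.12 with 4.6 (stopping or modifying radiotherapy), 8.1.3 (monitoring of adverse events), 9.1 (censoring) and 9.3 (analysis sets). The amendment need not, and should not, set any rule on when treatment stops.

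The cost is a few lines of text and the ethics submission required by section 12. The visits are already in the examination schedule. The protocol shows no budget, so the cost of following patients who would otherwise have left cannot be judged from it. Outcomes of patients already withdrawn may not be recoverable, so the change is worth making early.
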